We propose a two-arm cluster randomized controlled design, in which the unit of randomization is the clinician. Up to fifty cardiology clinicians will be randomly assigned to either the coaching intervention or to a control condition. We will recruit up to 50 clinicians to ensure that we have at least 40 clinicians with complete pre- and post-intervention measures. Although the unit of randomization is the clinician, the unit of evaluation is the patient: 10 patients per clinician (4 pre-intervention and 6 post-intervention) who get cardiology care from the enrolled clinicians will consent to audio-recording of their encounters and to completing the surveys. The intervention will be delivered in the clinic or via video-conference (Skype or Facetime), providing individual coaching and professional feedback on the communication behaviors encounters. We will also measure Press Ganey scores by clinician pre- and post-intervention. We will ask that learners (i.e. medical students, fellows, interns, etc.) not be in the room during recorded encounters with enrolled patient participants.

Pre-Intervention

We will work with the Duke Division Chief of Cardiology to recruit clinicians across Duke's ambulatory cardiology clinics. Enrolled clinicians will complete a baseline and demographics survey. Then, for each enrolled clinician, we will recruit and enroll 4 of their patients for baseline measures. Patients will be consented prior to the encounter. After consenting, they will be asked to complete a survey on a tablet in an application that uses REDCap to obtain demographic and health information. We will seek the patient's permission to access their medical record to obtain information about their cardiology care and health status. Patients will audio-record the encounter on a tablet that saves the audio-recording directly to REDCap. The audio-recording is not stored locally on the device. After the visit, patients will complete a survey on the tablet in REDCap with questions to measure communication quality of their interaction with the clinician and will complete the Interpersonal Processes of Care Survey. If a patient cannot complete this survey after the visit, we will call the participant to complete the survey over-the-phone, email the REDCap survey, or mail a paper copy to the patient. After patients complete the survey, their participation in the study is complete.

Randomization and Intervention

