General considerations: All variables will be described and explored using frequency tables, means, medians, standard deviations, histograms, box plots, and trajectory plots, both overall and within clinician. The primary analyses will be conducted on an intention-to-treat basis; clinicians and patients will be analyzed in the group to which they were randomized, regardless of clinician intervention adherence, using all available data. The main conclusions drawn from this trial will be based on the pre-specified hypotheses outlined below and will be tested with two-sided p-values at the standard 0.05 level. For all study outcomes, we will interpret differences between groups over time with reference to prior literature regarding clinically meaningful changes. Results from exploratory analyses will be interpreted with appropriate consideration for their exploratory nature. Statistical analyses will be performed using the latest release SAS for Windows (Cary, NC) and R/Rstudio.

The goal of the primary Hypothesis (1a) is to determine the efficacy of the clinician communication coaching intervention versus usual care on improvement in an objective measure of the quality of communication from baseline to post-training. Additionally, we are interested the intervention effect within Black patients and White patients separately. The quality of communication will be assessed at both baseline encounters and post-training encounters by a summary of clinician-encounter counts derived from the audio recordings. We plan to use mixed-effects models as our primary analytic strategy because they will appropriately account for the intracluster correlation of multiple patient encounters for each clinician and same clinicians followed over time. The mixed-effects model for Hypothesis 1a will have the following form: $\log(\mu_{ijk}) = \mu_0 + \mu_1(post) + \mu_2(post*int_k) + \mu_3(clinrace_k) + b_{0k} + b_{1kj}$, where Y_{ijk} is the number of quality communication statements for patient i at time j clustered within physician i , and Y_{ijk} is assumed to be Poisson with mean and variance equal to μ_{ijk} . The fixed effects in the model include indicator variables for the post-treatment ($post$), intervention group (int), and clinician race ($clinrace$). The random intercepts, b_{0k} and b_{1kj} , are normally distributed and account for dependence of encounters within clinicians, both between patients and on clinicians over time. PROC GLIMMIX (with

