A similar linear mixed-effects model (rather than a Poisson) model will be used to examine the reduction in racial disparities of quality of patient-centered care and test Hypothesis 2b. Note that in a linear model framework, the coefficients will represent differences in means rather than rate ratios.

Power and Sample Size Considerations: The effect of interest for Aims 1 and 2 is the relative difference in the post-period between the intervention and usual care groups; Aim 1 focuses on the overall difference and the difference within Black and White patients separately, while Aim 2 on the difference within Black patients compared to White patients. The sample size requirements are greatest for Aim 2; as discussed by Leon and Heo (2009), the needed

sample size for the patient race-by-intervention group interaction is 4 times that needed for the overall test. For Hypotheses 1a and 2a, our sample size calculations are based upon the difference between two Poisson rates (incident rate ratio) in a cluster randomized design (i.e., patients clustered within clinician).

Based on preliminary studies, the baseline mean number of quality communication statements is 1.0, and a conservative range of coefficients of variation (CV) is 0.2 to 0.5 to account for patients clustered within clinician. With a **sample size of 240 patients in the post period (6 per clinician)** and a type-I error of 5%, we will have 80% power to detect incident rate ratios of 1.5 to 1.8 for Hypothesis 1a in the overall test, 1.6 to 1.9 for Black or White patients separately, and 1.8 to 2.5 for Hypothesis 2a.

For hypotheses 1b and 2b, our sample size calculations are based upon the difference between two means in a cluster randomized design. We present a conservative range of intraclass correlation coefficients (ICC) to account for patients clustered within clinician. With a **sample size of 240 patients (6 per clinician)** and a type-I error of 5%, we will have 80% power to detect mean differences of effect size 0.37 to 0.44 for Hypothesis 1b in the overall test, 0.52 to 0.56 for Black or White patients separately, and 0.65 to 0.91 for Hypothesis 2b. PASS 15 was used for all calculations.

	Number of clinicians	Number of patients in the postintervention phase (number per clinician)	Hypothesis 1a and 2a: Incident Rate Ratio		Hypothesis 1b and 2b: Mean Effect Size	
			CV	Pre-post Relative Rate	ICC	Pre-post Difference

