Aim 1: Overall intervention versus usual care	40 (20 in each treatment arm)	240 (6 per clinician)	0.2 0.35 0.5	1.5 1.6 1.8	0.01 0.05 0.1	0.37 0.41 0.44
Aim 1: Racial subgroup intervention versus usual care	40 (20 in each treatment arm)	120 (3 per clinician)	0.2 0.35 0.5	1.6 1.8 1.9	0.01 0.05 0.1	0.52 0.54 0.56
Aim 2: Racial differences in intervention versus usual care	40 (20 in each treatment arm)	Effective sample size is 60 (1 or 2 per clinician)	0.2 0.35 0.5	1.8-2.2 1.9-2.3 2.1-2.5	0.01 0.05 0.1	0.65-0.91 0.66-0.91 0.67-0.91

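### The Aim 2 power row uses a between-clinician formula for a within-clinician interaction, so the ends of its printed ranges are not 80%-power effects

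*SAP*

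**What the plan says.** The SAP tests Aim 2 with a Poisson mixed model containing a Black-by-intervention term and one random effect, a clinician intercept (F.3 Aim 2 Analyses). Hypothesis 2b uses a similar linear model. The text names λ5 as the tested coefficient. In the printed equation λ5 multiplies clinician sex and the interaction is λ3. That is a separate labelling point, and I read the test as the interaction.

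The SAP power section says the interaction needs four times the sample of the overall test, and bases all calculations on two-group cluster-randomized comparisons. The Aim 2 table row has "40 (20 in each treatment arm") and "Effective sample size is 60 (1 or 2 per clinician"). It prints:

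- 2a, at CV 0.2 / 0.35 / 0.5: 1.8-2.2 / 1.9-2.3 / 2.1-2.5
- 2b, at ICC 0.01 / 0.05 / 0.1: 0.65-0.91 / 0.66-0.91 / 0.67-0.91

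The SAP text summarizes these as "1.8 to 2.5 for Hypothesis 2a" and "0.65 to 0.91 for Hypothesis 2b". Protocol F.5 gives the same 2b range, but 1.8 to 2.1 for 2a.

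**The concern.** Each clinician sees patients of both races: 6 in the post period, 3 per race in the table's own subgroup row. The interaction compares each clinician's Black-White gap between arms. Whatever shifts all of a clinician's encounters alike drops out of that gap, so between-clinician variation should not inflate the detectable effect. The table treats the interaction as a comparison of clinician means in a smaller sample, and lets ICC and CV inflate it.

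Both documents say Aim 2 has the largest sample-size requirement. This row is therefore where a reader looks to judge what disparity effect the trial could find. Someone who takes 0.65 or 1.8 as an 80%-power effect would overrate the trial's sensitivity.

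**Working it through.** **Inputs**

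- Significance: tests "will be tested with two-sided p-values at the standard 0.05 level" (Protocol, General considerations).
- Power: 80% (SAP: "type-I error of 5%, we will have 80% power to detect mean differences of effect size 0.37 to 0.44"). The normal multiplier is 1.960 + 0.842 = 2.80.
- Clinicians: 20 per arm. The Protocol covers dropout by over-recruiting: "We will recruit up to 50 clinicians to ensure that we have at least 40 clinicians with complete pre- and post-intervention measures".
- Post-period patients: "240 (6 per clinician"), hence 3 Black and 3 White per clinician and 60 encounters per race-by-arm cell.
- Baseline mean count: 1.0 (SAP power section).
- Not in the documents: the degrees of freedom (38 = 40 − 2 used here) and the four cell means for 2a.

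**Step 1. Reproduce the printed row.** 240/4 = 60, and 60/40 = 1.5 patients per clinician, bracketed by m = 2 and m = 1.

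- Means: SE = sqrt(2[1+(m−1)ICC]/(20m)), noncentral t with 38 df.
- Rates: 20 = 1 + 2.80²[(1+r)/m + CV²(1+r²)]/(r−1)², the cluster formula for Poisson rates, solved for r.

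| | m = 2 | m = 1 | Printed |
|---|---|---|---|
| 2b, ICC 0.01 | 0.646 | 0.909 | 0.65-0.91 |
| 2b, ICC 0.05 | 0.659 | 0.909 | 0.66-0.91 |
| 2b, ICC 0.10 | 0.674 | 0.909 | 0.67-0.91 |
| 2a, CV 0.2 | 1.81 | 2.19 | 1.8-2.2 |
| 2a, CV 0.35 | 1.92 | 2.30 | 1.9-2.3 |
| 2a, CV 0.5 | 2.09 | 2.47 | 2.1-2.5 |

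All twelve ends match. They are 80- and 40-patient between-clinician calculations.

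**Step 2. Hypothesis 2b as a within-clinician contrast.** A clinician's gap (3 versus 3) has variance 2(1−ICC)/3 in units of SD². Comparing 20 such gaps with 20 gives variance 2 × [2(1−ICC)/3]/20, so SE = SD × sqrt(4(1−ICC)/60).

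| ICC | SE | Detectable, normal | Detectable, t 38 df | Power at printed lower end (normal; t) | Power at 0.91 (normal; t) |
|---|---|---|---|---|---|
| 0.01 | 0.257 | 0.72 | 0.74 | 0.65: 72%; 69% | 94%; 93% |
| 0.05 | 0.252 | 0.71 | 0.72 | 0.66: 75%; 72% | 95%; 94% |
| 0.10 | 0.245 | 0.69 | 0.70 | 0.67: 78%; 76% | 96%; 95% |

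The detectable effect falls slightly as ICC rises, whereas the printed lower end rises.

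**Step 3. Hypothesis 2a.** The clinician effect multiplies both races' rates and cancels from the log ratio of rate ratios R. With 60 encounters per cell, SE = sqrt((sum of 1/cell mean)/60).

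- Other three cells at 1.0: log R = 2.80 × sqrt((3 + 1/R)/60) gives R = 1.97.
- Power at 1.8: SE = sqrt(3.556/60) = 0.243; 0.588/0.243 − 1.96 = 0.45, so about 68%.
- The same calculation gives about 75% at 1.9, 87% at 2.1, 91% at 2.2 and 97% at 2.5.
- Simulation with lognormal clinician effects gives 68/67/67% at 1.8 and 97/97/97% at 2.5 for CV 0.2/0.35/0.5, so CV hardly matters.

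Other assumed cell means:

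| Assumption | Detectable R | Power at 1.8 |
|---|---|---|
| White-patient effect 1.8, no control-arm gap | 1.84 | 77% |
| White-patient effect 1.5, no control-arm gap | 1.88 | 74% |
| Control-arm Black/White ratio 0.8, no White-patient effect | 2.04 | 63% |

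**The case against.** The strongest reply is that the row is a rough bracket and the bracket works. Much of this stands:

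- The corrected 2b value lies inside the printed range at every ICC. For 2a, 1.97 lies inside the ranges for CV 0.2 and 0.35.
- The effective sample of 60 is sound at ICC 0. Sixty independent patients, 30 per arm, give 2.80 × sqrt(2/30) = 0.723, and the within-clinician formula gives the same.
- The upper ends, and the whole CV 0.5 entry for 2a, err on the safe side.
- The printed figures follow from the formulas the SAP states, so the fault is the choice of formula and not a slip in calculation.
- No single 2a value is right without assumed cell means. The trial's own hypotheses expect both a treatment effect and an existing disparity.
- A null disparity result would be judged chiefly on the planned 95% confidence interval.

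A reader might infer that the whole printed range is wrong, or that the trial is materially underpowered for Aim 2. The documents support neither. They set no target disparity effect to fall short of, and the printed 2b range contains the correct answer.

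What the reply does not rescue is the claim of 80% power across the range. Ends with roughly 70% and 95% power are not 80%-power effects, and no choice of m within the bracket corrects the trend with ICC or CV.

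**Conclusion.** The point holds in limited form. The Aim 2 row answers a between-clinician question, while the planned test is a within-clinician contrast.

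- **2b:** the lower ends have about 72/75/78% power (69/72/76% with 38 df) and 0.91 has 93-96%. The design detects about 0.69-0.72 SD (normal) or 0.70-0.74 SD (t) at 80% power.
- **2a:** power at 1.8 is about 68% with the other cells at mean 1.0, and 63-77% over the other cell means tried. It is about 87% at 2.1, where the Protocol's range stops, and about 97% at 2.5, which only the SAP prints. The detectable ratio is about 1.84-2.04 and is practically the same at every CV.

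This rests on a 3/3 racial split per clinician, where the Protocol promises only about half Black patients in the sample overall. A random 50/50 split gives about 0.71-0.73 for 2b. It also rests on no variation between clinicians in the race gap, as the SAP's random-intercept model implies. With an assumed gap variance of 0.05 to 0.2 SD², 2b becomes 2.80 × sqrt(2[2(1−ICC)/3 + variance]/20), about 0.71 to 0.82.

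The consequence is modest: the favourable end of the range is somewhat too optimistic.

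**What to change.** Replace the Aim 2 table row and the matching sentences in the SAP power section and Protocol F.5 with one interaction calculation, worded alike in both documents:

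- 2b: SE = SD × sqrt(4(1−ICC)/60), detectable effect 0.72/0.71/0.69 (normal) or 0.74/0.72/0.70 (t, 38 df) at ICC 0.01/0.05/0.10. State which reference distribution is used.
- 2a: a detectable ratio of rate ratios of about 1.84-2.04 for all CVs, with the assumed cell means printed (1.97 if the other three cells have mean 1.0).
- Delete the entry of 1 or 2 patients per clinician.
- State the assumptions of a 3/3 split and a constant race gap, and give the 0.71-0.82 range as the sensitivity of 2b to the second.

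The cost is a table row and a few sentences. No patients are added and no test changes. The plan gives up only its most favourable figures.
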